8.3 Subsequent Assessments

All study visits and procedures are outlined in appendix B – the following details pertain to participants undergoing nasal challenge:

Visit 1 This visit will take place as close to a negative COVID test result. They will undergo a brief medical assessment including baseline physiological observations. They will then undergo nasal lavage followed by nasal curettage/brushing and blood sampling.

Subsequently, nasal challenge with saline (n=4) or R848 (n=20) will then be performed and non-invasive nasosorption samples will be taken every 2 hours until 8 hours after challenge. Physiological observations, total nasal symptom scores (TNSS) and peak nasal inspiratory flow (PNIF) will also be assessed 2-hourly. Blood will be collected for white blood cell differential and serum 4 hours after nasal challenge.

Participants can then choose to go home or have the option of remaining at the CCRC overnight as it has the facilities to provide this support (e.g. if the patient has travelled from further away).

Visit 2 This will take place at 24h with collection of nasosorption, curettage/brushing and a blood sample along with assessment of physiological observations, TNSS and PNIF.

For up to half the group who volunteered for an initial post-nasal space biopsy (6 weeks earlier), a second post-nasal biopsy will be undertaken. For these participants this will be the end of the study.

Visit 3 For the remaining half of the participants (n=12), they will undergo a second nasal challenge with saline (n=2) or R848 (n=10) to investigate mechanisms of innate immune memory in epithelial cells. All assessments and procedures will be identical to visit 1.

Visit 4 All study assessments and procedures will the same as visit 2.

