6.2 Primary Outcome Measure

1. Increase in CXCL10 nasal mucosal gene expression at 24 hours after nasal challenge with R848 compared to baseline

Secondary Outcome Measures

1. Difference in CXCL10 nasal mucosal gene expression at 24 hours after R848 challenge between healthy subjects and those with allergic rhinitis
2. Change in participant's temperature between first and second nasal challenge with R848 (as a marker of clinical tolerability)
3. Difference in CXCL10 nasal mucosal protein in nasal mucosal lining fluid over 24 hours expressed as area under curve (AUC) between first and second nasal challenge with R848.

Exploratory Outcome Measures

1. Difference in CXCL10 after ex-vivo stimulation of blood samples with LPS before and 24 hours after nasal challenge with R848
2. Single-cell gene expression and epigenetic profiles in mucosal tissue and blood before and after nasal challenge with R848
3. Comparison of single-cell and epigenetic profiles between healthy and allergic disease groups

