8. STUDY PROCEDURES

Pictures of the study procedures are outlined in appendix A and an outline of study procedures in relation to study visits is outlined in appendix B.

Nasal lavage: 10ml of normal saline will be administered and collected gently through a disposable plastic olive-shaped device into both nostrils prior to each challenge. This acts to “clean” the nasal mucosa of nasal debris prior to challenge and the nasal washing will be discarded.

Nasosorption: Nasal mucosal lining fluid will be collected non-invasively using nasosorption initially regularly (0min, 15min, 30min, 1h, 2h) then at two-hourly intervals (4h, 6h, 8h, 24h) after each challenge to assess the kinetics of interferon, cytokine and chemokine production.

Nasal mucosal epithelium: Nasal mucosal epithelial cells will be collected at the screening visit, baseline (0h) and 24 hours after each challenge to assess transcriptional and epigenetic signatures and to culture epithelial cells in the lab. Therefore, a maximum of up to three sets of samples per volunteer will be taken from half of the group undergoing single challenge (n=12), whilst the remainder of the group undergoing double challenge will have a total of five sets of samples taken (n=12). Up to five sets of nasal curettage samples were taken per volunteer in a prior study using R848 with good tolerability and no withdrawal of participants from the study¹⁵. Topical anaesthetic spray may be offered prior to procedures.

- **Nasal brushings** are taken using a small cytology brush from the nasal inferior turbinate – up to two samples will be taken (one from each nostril).
- **Nasal curettage** involves the use of a small plastic curette to gently “scrape” a small amount of tissue from the nasal inferior turbinate – up to four samples will be taken (two from each nostril).

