19. APPENDIX A: STUDY FLOWCHART

20. APPENDIX B: SCHEDULE OF PROCEDURES

Procedures	Visits				
	Screening	Visit 1 (duration 10h) 1 st nasal challenge	Visit 2 (at 24h) 1 st nasal challenge	Visit 3 (duration 10h) 2 nd nasal challenge	Visit 4 (at 24h) 2 nd nasal challenge
Informed consent	X				
Demographics, Medical History and Medications	X				
General physical examination	X				
ECG and Laboratory tests	X				
DNA blood test (up to 8.5mL)	X				
SARS-CoV-2 Lateral Flow or PCR nasal swab		X (negative test prior to nasal sampling)		X (negative test as close as possible to sampling)	
1 st Nasal challenge with saline (n=4) or R848 (n=20)		X			
2 nd Nasal challenge with saline (n=2) or R848 (n=10)				X	
Vital signs, clinical assessment and symptom scores		X (2 hourly)	X	X (2 hourly)	X
TNSS and PNIF		X (2 hourly)	X	X (2 hourly)	X
Nasal lavage		X (0h)		X (0h)	
Nasosorption (filter strips to absorb mucosal fluid)		X (15min, 30min, 1hr, 2hr, then 2 hourly)	X	X (15min, 30min, 1hr, 2hr, then 2 hourly)	X
Nasal curettage	X	X	X	X	X
Nasal brushing	X	X	X	X	X
Post-nasal space biopsy (a minimum of 6 weeks prior to challenge) and at visit 2	X		X		
Blood (9ml FBC, serum 0h, 4h, 24h), (13ml single cell analysis and Truculture at 0h and 24h)		X (0h and 4h)	X	X (0h and 4h)	X

TNSS Total Nasal Symptom Score; PNIF Peak Nasal Inspiratory Flow

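### The nasosorption schedule differs between section 8, section 8.3 and Appendix B, and only section 8 has a 0 min strip, so the repeat-challenge CXCL10 AUC may have no pre-challenge value

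*Combined protocol and SAP*

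**What the plan says.** The outcome is in section 6.2: the difference between the first and second R848 challenge in CXCL10 protein "in nasal mucosal lining fluid over 24 hours expressed as area under curve (AUC"). Section 11.1 compares the two AUCs within person by a paired Wilcoxon signed-rank test, with the hypothesis that the second response is larger. It also compares AUCs between healthy and allergic participants by a Mann-Whitney test. It gives no time grid, no AUC rule and no baseline handling.

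The strips behind the AUC are described in three places:

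- Section 8, Nasosorption: "initially regularly (0min, 15min, 30min, 1h, 2h) then at two-hourly intervals (4h, 6h, 8h, 24h) after each challenge".
- Section 8.3, Visit 1, before the spray: "They will then undergo nasal lavage followed by nasal curettage/brushing and blood sampling". After the spray: "non-invasive nasosorption samples will be taken every 2 hours until 8 hours after challenge". Visit 2: "This will take place at 24h with collection of nasosorption, curettage/brushing and a blood sample". Visit 3 is to repeat Visit 1, and Visit 4 to repeat Visit 2.
- Appendix B, nasosorption row, with the same entry at Visits 1 and 3: "X (15min, 30min, 1hr, 2hr, then 2 hourly"). There is a further mark at Visits 2 and 4 and none at screening.

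In Appendix B the lavage row is marked 0h, and the blood row reads "9ml FBC, serum 0h, 4h, 24h), (13ml single cell analysis and Truculture at 0h and 24h"). The nasosorption row carries no 0h.

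**The concern.** The three places do not ask for the same samples, and the strip on which they differ most consequentially is the one taken before the spray. The repeat-challenge comparison is meant to show whether a first exposure changes the response to a second. By Visit 3 a participant has had one R848 challenge and, under Appendix B, curettage and brushing at screening, Visit 1 and Visit 2. If resting CXCL10 in the lining fluid were still raised for any of those reasons, a raw AUC would rise in the direction of the hypothesis even if the response to the second spray were unchanged. A pre-challenge strip at each visit is what would let the two be separated. If it is not taken on the day, no later analysis can supply it.

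**Working it through.** The plan states no figure for this outcome, so there is nothing to reproduce. The check is a comparison of the time points, followed by some algebra and an illustration on assumed inputs.

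**1. Time points per challenge**

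| Source | Strips (h) | Count | Span | 0 min |
|---|---|---|---|---|
| Section 8 | 0, 0.25, 0.5, 1, 2, 4, 6, 8, 24 | 9 | 24 of 24 h | yes |
| Appendix B, stopping at 8 h | 0.25, 0.5, 1, 2, 4, 6, 8, 24 | 8 | 23.75 of 24 h (99.0%) | no |
| Appendix B, running to the 10 h visit length | as above plus 10 | 9 | 23.75 of 24 h (99.0%) | no |
| Section 8.3, read literally | 2, 4, 6, 8, 24 | 5 | 22 of 24 h (91.7%) | no |

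Section 8.3 refers to Appendix B for procedures. That can restore the 15 min to 1 h strips, but not 0 min, because Appendix B lacks it too. Appendix B has no nasosorption at screening. Under that table, the last strip before the second challenge is therefore the 24 h strip of the first, about two weeks earlier.

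**2. What a missing 0 min strip leaves unresolved**

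Write the raw AUC at the first challenge as resting part plus response. Let s be the resting share of that AUC and d the relative rise in the resting level by Visit 3, assumed to last the full 24 h, with the response unchanged. Then

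AUC(second) / AUC(first) = 1 + s × d.

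The documents give neither s nor d. With assumed values:

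- s = 0.40, d = 0.25: 0.40 × 0.25 = 0.10, a 10% rise.
- s = 0.20, d = 0.25: 0.20 × 0.25 = 0.05, a 5% rise.
- s = 0.60, d = 0.50: 0.60 × 0.50 = 0.30, a 30% rise.

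These show the mechanism only. They are not estimates for this trial.

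**3. Whether the first post-challenge strip can stand in for baseline**

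Assumed curve: C(t) = 1 + 9(t/p)exp(1 − t/p), with peak time p, trapezoidal rule, and incremental AUC = total AUC − (span × first strip). For p = 4 h:

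- Section 8: 137.0 − 24 × 1 = 113.0.
- Appendix B to 8 h: C(0.25) = 2.436, so 136.5 − 23.75 × 2.436 = 78.7 (to rounding).
- Section 8.3: C(2) = 8.419, so 126.3 − 22 × 8.419 = −58.9.

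Across the peak times tried (1, 2, 4, 6, 8 and 12 h), the section 8 figure runs from 25.6 to 161.9. Appendix B runs from −88.2 to 150.0 and is negative for peaks at 1 and 2 h. Section 8.3 runs from −152.3 to 82.4 and is negative for peaks at 1 to 4 h. On this curve a post-challenge strip is not a safe substitute.

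**4. Total AUC on the different grids, same assumed curve**

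Relative to section 8, the total AUC is 0.68 to 0.97 under section 8.3, 0.98 to 1.00 under Appendix B to 8 h, and 0.92 to 1.03 under Appendix B to 10 h. If both challenges in a person use the same grid and the curve keeps its shape, this factor cancels in the paired comparison. It matters only if grids differ between people or visits.

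**The case against.** The strongest reply is that this is loose drafting around one intended schedule. Sections 8 and Appendix B agree on 15 min, 30 min, 1 h, 2 h and two-hourly strips thereafter, plus 24 h, and section 8.3 is a visit narrative that points to the table. That has force: the five-strip reading of section 8.3 is probably not intended. It does not answer the missing 0 min strip, which is absent from both the narrative and the table, while neighbouring rows of the table are marked 0h.

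Four stronger readings are tempting, and the documents do not support them:

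- **That a person's two challenges would be sampled on different grids.** Section 8.3 makes Visit 3 the same as Visit 1, and Appendix B has one entry for both. Whichever place is followed, the paired grid should match. Differing grids within a person are a minor risk.
- **That section 8 has no baseline strip either, because its list is described as following each challenge.** Elsewhere section 8 uses 0h for baseline and for blood taken before challenge, so 0 min most naturally means the same. It still needs stating, with its place relative to lavage and curettage.
- **That the AUC cannot be calculated without a baseline, or that a baseline-corrected AUC must be the main analysis.** A total AUC needs no pre-challenge value, and neither section 6.2 nor section 11.1 promises correction. In a study of innate immune memory, a raised resting level could be part of the effect of interest. Subtracting a single strip also adds noise with only 10 repeat R848 challenges planned.
- **That carry-over at two weeks is likely.** The documents give no resting CXCL10 levels and no evidence either way.

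Section 11.1 also says the analysis follows the previous R848 publication, which may define the AUC. That publication is not available here, and no analysis rule can replace a strip that was not taken.

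**Conclusion.** The point holds as an inconsistency about which samples are collected: nine strips with 0 min in section 8, eight or nine without it in Appendix B, and five without it in section 8.3 read literally. Under two of the three descriptions there is no pre-challenge CXCL10 protein value at either challenge, and a raised resting level at Visit 3 could not be separated from a larger response. It bears on one secondary outcome and on the cytokine AUC comparison between groups. The primary outcome, gene expression at 24 hours, is not affected. The size of any distortion cannot be derived from the documents; the percentages and AUC values above rest wholly on assumed resting shares, shifts and curve shape. It is worth correcting because the loss would be permanent and the correction is small.

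**What to change.** 1. Reconcile the three places to the section 8 list. Add 0 min and the last two-hourly time to the nasosorption row of Appendix B and to the section 8.3 text, for Visits 1 and 3.
2. State that the 0 min strip is taken before the spray, and at the same point relative to lavage and curettage at both visits.
3. In section 11.1, name the time points and the AUC rule. Keep the planned AUC over 24 h, and report the AUC above the 0 min level of the same challenge as a supporting analysis. Which AUC is the main one is for the sponsor to choose and record before the data are examined.

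The cost is wording in sections 8, 8.3 and 11.1 and in Appendix B, plus one further calculation per cytokine. No strip is added beyond those section 8 already lists. For any challenge already done without a 0 min strip, the value cannot be recovered, and the supporting analysis should report how many participants lack it.

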8.4 Definition of End of Trial

The end of trial is the date of the last visit of the last participant.

8.5 Discontinuation/Withdrawal of Participants from Study Treatment

Each participant has the right to withdraw from the study at any time. In addition, the investigator may discontinue a participant from the study at any time if the investigator considers it necessary for any reason including:

- Ineligibility (either arising during the study or retrospective having been overlooked at screening)
- Significant protocol deviation
- Significant non-compliance with treatment regimen or study requirements
- An adverse event which requires discontinuation of the study or results in inability to continue to comply with study procedures
- Consent withdrawn

The reason for withdrawal will be recorded in the CRF. If the participant is withdrawn due to an adverse event, the investigator will arrange for follow-up visits or telephone calls until the adverse event has resolved or stabilised.

8.6 Source Data

Source documents are original documents, data, and records from which participants' CRF data are obtained. These include, but are not limited to, hospital records (from which medical history and previous and concurrent medication may be summarised into the CRF), clinical and office charts, laboratory and pharmacy records, diaries, microfiches, radiographs, and correspondence.

CRF entries will be considered source data if the CRF is the site of the original recording (e.g., there is no other written or electronic record of data). All documents will be stored safely in confidential conditions. On all study-specific documents, other than the signed consent, the participant will be referred to by the study participant number/code, not by name.

9. TREATMENT OF TRIAL PARTICIPANTS

9.1 Description of Study Treatment

Challenge Agent	Manufacturer	Catalogue Dose	Production Purity
Resiquimod (R848) VacciGrade TLR7/8 agonist Synthetic vaccine grade	Invivogen, California [name] www.invivogen.com	5 mg lyophilized R848 Reconstitute in endotoxin-free physiological water CAS 144875-48-9	Non-biological origin: does not contain any animal nor human components. Endotoxin <1.25 EU/mg

9.2 Storage of Study Equipment or Related apparatus

R848 will be stored in labelled storage vials in the laboratory freezer and defrosted on the day of usage. Saline will be stored at room temperature. All other clinical equipment will be stored either in the PI's laboratory or the CRF.

9.3 Compliance with Study Treatment

Participants will be administered saline or R848 via a nasal spray directly by the investigators and therefore there will be no issues in assessing compliance.

10. SAFETY REPORTING

10.1 Definitions

10.1.1 Adverse Event (AE)

An AE or adverse experience is any untoward medical occurrence in a participant, which does not necessarily have to have a causal relationship with the intervention. An AE can therefore be any unfavourable and unintended sign (including an abnormal laboratory finding), symptom or disease temporally associated with the study, whether or not considered related to the study.

10.1.2 Serious Adverse Event (SAE)

A serious adverse event or reaction is any untoward medical occurrence that at any dose:

- Results in death,
- Is life-threatening,

NOTE: The term "life-threatening" in the definition of "serious" refers to an event in which the participant was at risk of death at the time of the event; it does not refer to an event which hypothetically might have caused death if it were more severe, including an event which:

- Requires inpatient hospitalisation or prolongation of existing hospitalisation,
- Results in persistent or significant disability/incapacity, or
- Is a congenital anomaly/birth defect.
- Other important medical events*

*Other events that may not result in death, are not life threatening, or do not require hospitalisation, may be considered a serious adverse event when, based upon appropriate medical judgement, the event may jeopardise the patient and may require medical or surgical intervention to prevent one of the outcomes listed above.

Planned admission to hospital for a pre-existing condition will not be considered an SAE.

10.1.4 Suspected Unexpected Serious Adverse Reactions (SUSAR)

A serious adverse reaction, the nature or severity of which is not consistent with the applicable product information

10.2 Reporting Procedures for All Adverse Events

All AEs occurring during the study observed by the investigator or reported by the participant, whether or not attributed to study, will be recorded on the CRF.

The following information will be recorded: description, date of onset and end date, severity, assessment of relatedness to study, other suspect device and action taken. Follow-up information should be provided as necessary.

AEs considered related to the study as judged by a medically qualified investigator or the sponsor will be followed until resolution or the event is considered stable. All related AEs that result in a participant's withdrawal from the study or are present at the end of the study, should be followed up until a satisfactory resolution occurs.

It will be left to the investigator's clinical judgment whether or not an AE is of sufficient severity to require the participant's removal from treatment (see section 7.7). A participant may also voluntarily withdraw from treatment due to what he or she perceives as an intolerable AE. If either of these occurs, the participant must undergo an end of study assessment and be given appropriate care under medical supervision until symptoms cease or the condition becomes stable. The relationship of AEs to the study will be assessed by a medically qualified investigator.

10.3 Reporting Procedures for Serious Adverse Events

All SAEs, except those expected ones defined in section 10.1.3 that do not require immediate reporting, must be reported to the Sponsor within one working day of discovery or notification of the event. The Sponsor will perform an initial check of the information and ensure that it is reviewed at the next R&D Management meeting. All SAE information must be recorded on an SAE form and sent to the Sponsor using

the appropriate reporting form and the contact details on there. Additional information received for a case (follow-up or corrections to the original case) needs to be detailed on a new SAE form which must be sent to the Sponsor using the appropriate reporting form and the contact details on there.

The Sponsor will report all SUSARs to the Research Ethics Committee concerned. Fatal or life-threatening SUSARs must be reported within 7 days and all other SUSARs within 15 days. The PI will inform all investigators concerned of relevant information about SUSARs that could adversely affect the safety of participants. In addition to the expedited reporting above, the PI shall submit once a year throughout the study or on request an Annual Report to the Ethics Committee which lists all SAEs / SUSARs that have occurred during the preceding 12 months.

11. STATISTICS

11.1 Description of Statistical Methods

This is an open label interventional trial to investigate basic mechanisms of innate immunity. The following data outputs will be generated:

- Single-cell transcriptomic signatures
- Epigenetic signatures
- Nasal and blood cytokine levels

This data is typically of a non-parametric distribution and the statistical plan will follow a similar template to the previous publication using R848 challenge (15). For the single-cell and epigenetic datasets, a series of pre-processing quality control checks will take place followed by cell and gene-level downstream analysis with the support of specialised bioinformaticians.

For protein analysis, data will be plotted for individual cytokines using raw data at an individual level. For the repeat R848 challenge, area under curve (AUC) values will be calculated for each cytokine and paired Wilcoxon signed-rank test will be used to compare differences between each challenge with the hypothesis that repeat R848 challenge causes increased responses on secondary challenge.

AUC values of cytokine production after R848 challenge will also be compared between healthy and allergic participants using unpaired Mann-Whitney test.

11.2 The Number of Participants

In the prior publication using R848 nasal challenge (15), 12 participants in each group (healthy, allergic rhinitis and asthma) were sufficient to see differences in bulk gene expression and immune mediators in the nasal mucosa. The present study is based on utilising a powerful single-cell transcriptomic approach which is able to distinguish differences in immune responses at an individual cellular level. It may therefore be possible to see differences between groups in fewer numbers of participants but will allow recruitment of up to 12 participants in each group.

11.3 The Level of Statistical Significance

A P-value of < 0.05 will be taken to indicate statistical significance.

11.4 Procedure for Accounting for Missing, Unused, and Spurious Data.

Missing clinical data points will be imputed as the mean of values from that volunteer.

